4.3. Inclusion of Women and Minorities

Men and women, regardless of race, ethnic group or sexual orientation are eligible for this study.

4.4. Participant Registration

Participants may be registered from 8:00 am to 4:00 pm EST excluding holidays by emailing the Investigator-Sponsored Research Unit (ISRU) at: [contact]. Eligible participants will be entered on study centrally once the following items have been received by email:

- Completed registration form
- Consent and HIPAA signature pages
- Eligibility checklist

Following registration, participants must begin protocol treatment within 14 calendar days of registration. Issues that would cause treatment delays must be discussed with the Sponsor-Investigator. If a registered participant does not receive protocol therapy following registration, the participant will be recorded as withdrawn from study. The Study Monitor must be notified as soon as possible if a participant does not begin protocol treatment as scheduled. For additional registration questions, please email [contact] or call [contact].

The FCCC ISRU will notify the site by email once registration is confirmed and the sequence number has been assigned. Participants must be registered and have received a sequence number prior to the initiation of treatment.

Exceptions to the current registration policies will not be permitted.

5.0 **Treatment Plan**

Patients will be treated with Everolimus for 4, 28 day cycles. At the end of the fourth cycle, patients who have experienced a partial response (PR) defined as a reduction of 25% or more will continue therapy for an additional 2 cycles.

Patients will be treated continuously barring toxicity related delays. Missed days will not be made up. Patients will document adherence in a pill diary and should be directed to contact their treating physician with the onset of any side effects for further direction.

5.1. **Treatment Administration Tables**

Treatment Administration				
Agent	Dose	Route	Schedule	Length
Everolimus	10 mg	Oral	Daily	4 Cycles

If \geq 25% volume reduction and no new AMLs are seen after 4 Cycles, continue as follows:				
Agent	Dose	Route	Schedule	Length
Everolimus	10 mg	Oral	Daily	2 Cycles

5.2. **Duration of Therapy**

Patients will receive no more than 6 cycles of therapy in total.

5.3. **Duration of Follow up**

Patients will be followed for 1 year from the initiation of treatment for radiographic evaluation of their AML(s). Thus, maximum time on trial is 12 months. Patients who stop receiving Everolimus due to unacceptable adverse events will still be followed until the end of the study.

5.4. **Criteria for Discontinuation**

Patients will be removed from treatment if one of the following criteria applies:

- Disease progression including:
 - Bleeding or pain
 - Requirement for surgical or percutaneous intervention
 - Greater than a 25% increase in tumor volume of AML
- Intercurrent illness that prevents further administration of treatment

- Unacceptable adverse events
- Treatment is temporarily held for > 21 days
- Patient becomes pregnant
- Patient decides to withdraw from the study
- General or specific changes in the patient's condition that render the patient unacceptable for further treatment in the judgment of the investigator.

The reason for discontinuation and the date the patient was removed must be documented in the medical record and case report form.

5.5. **Optional Tissue and Blood Collection for Exploratory Objectives**

At time of trial initiation, patients will be consented to allow the use of their tissue and blood for future research, specifically including, but not limited to, the analysis of mTOR alterations, VEGF pathways and tumor genome sequencing (e.g. mutations (AKT/PI3K, PTEN), amplifications, deletions in TSC1 and TSC2).

At screening, if archival biopsy tissue of the AML is available, unstained slides will be requested. If a patient undergoes a clinical procedure where tissue will be obtained during the study, that tissue will also be collected for exploratory objectives. Biopsy, resection, and/or percutaneous intervention will be performed entirely at the discretion of the treating clinician based on individual clinical scenarios and needs.

An EDTA and red top tube will be collected to provide plasma, serum and peripheral blood mononuclear cells (PBMCs). All biological samples will be stored at Fox Chase Cancer Center for possible future research.

6.0 Dosing, Toxicity and Specific Adverse Events

6.1. **Dosing regimen**

Everolimus should be taken orally once daily at the same time every day, either consistently with or consistently without food

The tablets should be swallowed whole with a glass of water and should not be chewed or crushed. For patients unable to swallow tablets, the tablet(s) should be dispersed completely in a glass of water (containing approximately 30 mL) by gently stirring, immediately prior to drinking. The glass should be rinsed with the same volume of water and the rinse completely swallowed to ensure the entire dose is administered.

If vomiting occurs, no attempt should be made to replace the vomited dose. Patients should be instructed that if they miss a dose on one day, they must not take any extra dose the next day, but instead to immediately contact the study center as soon as possible to ask for advice.

6.2. Description of selected adverse drug reactions

In clinical trials and post-marketing spontaneous reports, everolimus has been associated with serious cases of the following:

- Hepatitis B reactivation, including fatal outcome.
- Reactivation of infections is an expected event during periods of immunosuppression.
- Renal failure events (including fatal ones) and proteinuria. Monitoring of renal function is recommended.
- Amenorrhea (including secondary amenorrhea).
- Pneumocystis jirovecii pneumonia (PJP) some with a fatal outcome.
- Angioedema has been reported with and without concomitant use of everolimus and ACE inhibitors

6.3. Dose modifications

For patients who do not tolerate the protocol-specified dosing schedule, dose adjustments are permitted in order to allow the patient to continue the study treatment. If multiple toxicities are experienced, dose modifications will be based on the toxicity requiring the largest dose reduction. Once dose is reduced, patients will continue at new dose. No dose re-escalations are allowed. Details of study treatment schedule adjustments for Everolimus-related toxicities and dose levels are provided in the below tables.

6.3.1. Dose adjustments and dose levels:

Dose level	Dose and schedule
0 (starting dose)	10mg
1	5mg
2	5mg every other day

If a patient has already decreased 2 dose levels, no further dose reduction is permitted. Patients who need an additional dose reduction will be required to discontinue everolimus.

6.3.2. Non-hematologic toxicities

Toxicity	Action
Non-Infectious Pneumonitis	Please refer to 6.3.4 .
AST or ALT elevation Grade 1 (> ULN - 3.0 x ULN) Grade 2 (> 3.0 - 5.0 x ULN)	
 • Maintain current dose level
AST or ALT elevation Grade 3 or higher (> 5.0 ULN)*	
 • Discontinue study drug permanently
Intolerable grade 2 mucositis,	
 • Interrupt everolimus administration until resolution to \leq grade 1 or baseline grade / value. • If resolution occurs within ≤ 7 days, everolimus should be re-started at the dose level prior to interruption. • If resolution takes > 7 days, or if event recurs within 28 days, hold everolimus until recovery to \leq grade 1 or baseline grade / value and reintroduce everolimus at one dose level lower, if available. • Patients will be withdrawn from the study if they fail to recover to \leq grade 1 or baseline grade / value within 21 days.
Recurrence of intolerable grade 2 mucositis	
 • Reduce dose to the next lower dose level, if available.
Grade 2 hyperlipidemia or hypertriglyceridemia	
 • Reduce dose to the next lower dose level, if available. • If a patient is at the lowest dose of study drug, the drug may be held for ≤ 21 days to allow treatment and if the level returns to a grade 1 or lower, treatment can be resumed with a reevaluation monthly • See management of hyperlipidemia and hypertriglyceridemia and hyperglycemia below
Grade 2 hyperglycemia	
 • Adjust medications as medically appropriate and re-evaluate at next visit • If after medical adjustment grade 2 dysfunction persists, reduce dose to the next lower dose level, if available. • If a patient is at the lowest dose of study drug, the drug may be held for ≤ 21 days to allow treatment and if the level returns to a grade 1 or lower, treatment can be resumed with a reevaluation monthly • See management of hyperglycemia below

Toxicity	Action
Grade 3 or higher hyperglycemia or hypertriglyceridemia or hyperlipidemia	
 Discontinue study drug permanently
Grade 3 or higher clinical liver failure (asterixis or encephalopathy/coma)	
 Discontinue study drug permanently
Grade 3 or higher skin toxicity	
 Discontinue study drug permanently
Grade 3 or higher Diarrhea	
 Discontinue study drug permanently
Any other grade 3 toxicity	
 Interrupt everolimus administration until resolution to \leq grade 1 or baseline grade / value. If resolution occurs within ≤ 7 days, everolimus should be re-started at the dose level prior to interruption. If resolution takes > 7 days, or if event recurs within 28 days, hold everolimus until recovery to \leq grade 1 or baseline grade / value and reintroduce everolimus at one dose level lower, if available. Patients will be withdrawn from the study if they fail to recover to \leq grade 1 or baseline grade / value within 21 days.
Recurrence of a grade 3 toxicity after dose reduction	
 Reduce dose to the next lower dose level, if available.
Any other grade 4	
 Discontinue study drug permanently

6.3.3. Hematologic toxicities

Toxicity	Action
Grade 2 thrombocytopenia (platelets $<75, \geq 50 \times 10^9/L$)	
 No action
Grade 3 thrombocytopenia (platelets $<50, \geq 25 \times 10^9/L$)	
 Interrupt everolimus until resolution to grade ≤ 1 If resolution occurs ≤ 7 days, reintroduce everolimus at the dose level prior to interruption. If resolution occurs > 7 days, or event occurs within 28 days, reintroduce everolimus at one dose level lower, if available.
Grade 4 thrombocytopenia (platelets $< 25 \times 10^9/L$)	
 Discontinue study drug permanently

Grade 3 neutropenia or anemia (neutrophil <1, $\geq 0.5 \times 10^9/L$)	
 Interrupt everolimus until resolution to grade ≤ 1 or baseline value If AE resolution occurs ≤ 7 days, reintroduce everolimus at the same dose level. If AE resolution occurs > 7 days, or event occurs within 28 days, reintroduce everolimus at one dose level lower, if available.
Grade 4 neutropenia or anemia	
 Discontinue study drug permanently
Febrile neutropenia	
 Interrupt everolimus until resolution to grade ≤ 1 (or baseline value) and no fever. Reintroduce everolimus at one dose level lower, if available.
Recurrence of grade 3 toxicity after dose reduction	
 Reduce dose to the next lower dose level, if available.

6.3.4. Non-infectious Pneumonitis

Worst grade pneumonitis	Required investigations	Management of pneumonitis	Everolimus dose adjustment
Grade 1	CT scans with lung windows.	No specific therapy is required	Stop study drug permanently.
Grade 2	CT scan with lung windows. Consider pulmonary function testing includes: spirometry, DLCO, and room air O ₂ saturation at rest. Consider a bronchoscopy with biopsy and/or BAL. Monitoring at each visit until return to \leq grade 1. Return to initial monitoring frequency if no recurrence.	Symptomatic only. Consider corticosteroids and/or other supportive therapy if symptoms are troublesome.	Rule out infection and stop study drug permanently.
Grade 3	CT scan with lung windows and pulmonary function testing includes: spirometry, DLCO, and room air O ₂ saturation at rest. Monitoring at each visit until return to \leq grade 1. Return to initial monitoring frequency if no recurrence. Bronchoscopy with biopsy and/or BAL is recommended.	Consider corticosteroids if infective origin is ruled out. Taper as medically indicated.	Rule out infection and stop study drug permanently.
Grade 4	CT scan with lung windows and required pulmonary function testing, if possible, includes: spirometry, DLCO, and room air O ₂ saturation at rest. Monitoring at each visit until return to \leq grade 1. Return to initial monitoring frequency if no recurrence. Bronchoscopy with biopsy and/or BAL is recommended if possible.	Consider corticosteroids if infective origin is ruled out. Taper as medically indicated.	Rule out infection and stop study drug permanently..

6.4. Management of specific toxicities

Overall, safety data available from completed, controlled and uncontrolled studies indicate that everolimus is generally well tolerated at weekly or daily dose schedules. The safety profile is characterized by manageable adverse events (AEs). These AEs are generally reversible and non-cumulative¹⁷.

Adverse events most frequently observed with everolimus are rash, stomatitis /oral mucositis, non-infectious pneumonitis, fatigue, headache, anorexia, nausea, vomiting, diarrhea, and infections. Overall, the most frequently observed laboratory abnormalities include neutropenia, thrombocytopenia, hypercholesterolemia, and/or hypertriglyceridemia. The majority of these AEs have been of mild to moderate severity (NCI CTC grade 1-2).

6.4.1. Hepatitis B Reactivation

In the case of reactivation of Hepatitis B even in the face of pre-study screening, the trial will be immediately terminated and appropriate Hepatitis B therapy initiated.

6.4.2. Infections

Everolimus has immunosuppressive properties and may predispose patients to bacterial, fungal, viral or protozoal infections, including infections with opportunistic pathogens. Localized and systemic infections, including pneumonia, other bacterial infections, invasive fungal infections, such as aspergillosis or candidiasis and viral infections including reactivation of hepatitis B virus, have been described in patients taking Everolimus. Some of these infections have been severe (e.g. leading to respiratory or hepatic failure) and occasionally have had a fatal outcome. While taking Everolimus, be vigilant for symptoms and signs of infection; if a diagnosis of infection is made, institute appropriate treatment promptly and treatment will be permanently discontinued with everolimus. Referral for immediate and appropriate treatment will be made.

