3.0 Study Plan

After confirming eligibility criteria, patients will be enrolled in this study. Volumetric and perfusion/vascularity analyses will be done by DCE-MRI at baseline. Patients will then receive everolimus 10 mg daily. Treatment duration will be continuous for 4 cycles unless treatment is discontinued.

After 4 cycles of treatment, repeat imaging with DCE-MRI will be performed to assess tumor size kinetics (sum of volumes of all target AMLs identified at baseline). If the tumor has decreased in size by greater than or equal to 25% and no new AMLs greater than 1 cm in longest diameter have appeared, then the drug will be continued for another two cycles (6 cycles total treatment). If on the other hand the tumor has grown or decreased by less than 25% or there are new AMLs (at least 1 cm in longest diameter), then the drug will be discontinued.

At the end of cycle 6 and 12 months after start of therapy with everolimus, imaging via DCE MRI will be repeated to assess growth/regrowth kinetics/qualitative perfusion.

If for any reason a patient terminates treatment with everolimus earlier than the end of cycle 4, all imaging will still be performed and used for the statistical analysis and primary endpoint calculations. Given that therapy with everolimus has potential toxicity and that the disease in question (sporadic AML) is not a malignant condition, patients will not be replaced if they drop out, in a way signaling that the therapy may not be feasible. If a patient receives at least one dose of everolimus they will be included in the analysis. If a patient does not get imaged after 4 cycles of treatment, for the purposes of statistical considerations they will be considered a non-responder.

Treatment related toxicities and QOL will be assessed at baseline, day 1 of each 28 day cycle, at drug discontinuation and at the last study visit

Tissue for exploratory objectives will be collected at baseline only if available from archival tissue. Additional tissue will also be collected if the patient undergoes a partial or complete nephrectomy or embolization during the study period for the AML. Serum at baseline will also be collected for cfDNA and other future potential correlative studies.

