12.0 Statistical Considerations

12.1. Study Design/Endpoints

The required sample size for this trial is 43 patients, using a Simon two-stage design. The sample size justification and details are below.

We will conduct a single arm Phase II study to assess the efficacy of everolimus in patients with ≥ 3 cm sporadic AMLs. Response for a patient will be defined by a decrease in size of $\geq 25\%$ after 4 cycles of treatment.

We will implement an optimal two-stage Simon design for this trial. The new treatment would be of interest if the proportion, p , of responding patients is at least 25%. A proportion of patients with a response rate of less than 10% will be of no interest. Forty three (43) patients will allow us to test the null hypothesis: $p \leq 10\%$ against the alternative hypothesis: $p \geq 25\%$ at the 5% level of significance (α) with 80% power for a one-sided test. The early stopping point is 18 patients for both efficacy and toxicity. For efficacy, if 2 or fewer patients respond among the first 18 patients then the null hypothesis will not be rejected and the trial will be terminated. The probability of early stopping under the null is 73%. If the trial progresses until 43 patients are evaluated and 8 or more patients respond, then the null hypothesis will be rejected.

For toxicity, the trial will be paused and termination considered if out of the first 18 patients, 3 or more come off trial due to any adverse events as defined in the protocol. If the study proceeds to stage II (total enrollment = 43 patients), the trial will be paused and termination considered if at any point 8 or more patients come off trial due to any adverse events as defined in the protocol. If the true rate of any adverse events necessitating a patient to come off trial is 20%, the probability of early stopping is 73%; if the true rate of any adverse events necessitating a patient to come off trial is 5%, the probability of early stopping is 6%. Pause and

termination consideration for toxicity will occur, either early or finally, with probability 81% if true toxicity proportion is 20%; and 6% if it is 5%.

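### Infection has two incompatible dosing instructions (6.4.2 against 6.3.2), and the 12.1 toxicity rule counts patients who leave the trial although most adverse-event stops are only stops of drug

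*Combined protocol and SAP*

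**What the plan says.** **Infection.** Section 6.4.2 instructs that "if a diagnosis of infection is made, institute appropriate treatment promptly and treatment will be permanently discontinued with everolimus". It sets no grade limit. The table in 6.3.2 has no row for infection and no reference to 6.4.2, although its pneumonitis row does point to 6.3.4. What remains for a grade 3 infection is the row "Any other grade 3 toxicity". Under that row the drug is interrupted and, if the event resolves within 7 days, "everolimus should be re-started at the dose level prior to interruption"; after slower resolution or recurrence within 28 days it is reintroduced one dose level lower.

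Two other places bear on infection:
- The last bullet of 6.4.4 permits topical antifungal preparations and takes the patient off study only if a systemic agent is needed.
- The febrile neutropenia row in 6.3.3 restarts everolimus one level lower after recovery and does not mention infection.

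**Toxicity rule.** Section 12.1 pauses the trial and considers termination if, among the first 18 patients, "3 or more come off trial due to any adverse events as defined in the protocol", or if 8 or more of 43 do so. Its operating characteristics refer to the same event: "If the true rate of any adverse events necessitating a patient to come off trial is 20%, the probability of early stopping is 73"%.

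The follow-up sections say something different about such patients. Section 5.3: "Patients who stop receiving Everolimus due to unacceptable adverse events will still be followed until the end of the study". Section 3.0: "If for any reason a patient terminates treatment with everolimus earlier than the end of cycle 4, all imaging will still be performed". Section 5.4 lists unacceptable adverse events among the reasons for removal from treatment, not from the trial.

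**The concern.** A dose table should give one answer for one event. Here, two sites that each follow the text could manage the same grade 3 infection in opposite ways: one stops an immunosuppressant for good, the other restarts it at the same dose. The event is foreseeable, since 1.5 lists pneumonia and viral gastroenteritis among the most frequent grade 3/4 reactions in the tuberous sclerosis population.

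The second point is the tally itself. The rule in 12.1 is the only numerical toxicity boundary in the plan, and the event it counts is not defined. If leaving the trial is taken literally, most patients who stop drug for an adverse event have not left it. The two points meet in the count: the infected patient at the first site may add one to the tally, and the patient at the second may not. One patient is one of the 3 needed in the first 18, or one of the 8 needed in 43.

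**Working it through.** **1. The plan's own figures.** Let q be the true rate of the counted event. Boundaries and sample sizes come from 12.1.

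- Early pause: P(X ≥ 3), with X ~ Binomial(18, q).
- Early or final pause: P(X ≥ 3) + Σ over k = 0, 1, 2 of P(X = k) × P(Y ≥ 8 − k), with Y ~ Binomial(25, q).

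At q = 20% the early term is 0.7287. The final term is 0.0180 × 0.1091 + 0.0811 × 0.2200 + 0.1723 × 0.3833 = 0.0858, so the total is 0.8145. At q = 5% the results are 0.0581 and 0.0584. The plan states 73% and 81% at 20%, and 6% and 6% at 5%. All four are reproduced.

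| q | Early (3 of 18) | Early or final |
|---|---|---|
| 5% (plan) | 5.8% | 5.8% |
| 8% | 17.0% | 17.5% |
| 10% | 26.6% | 27.9% |
| 15% | 52.0% | 57.5% |
| 20% (plan) | 72.9% | 81.4% |

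The 8% row uses the latest adverse-event discontinuation figure in 1.5 (9 of 112 who received everolimus, 9/112 = 8.0%). It comes from another population and is a reference point, not a forecast. The 10% and 15% rows are assumed.

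**2. Which stops a literal count would include.**

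| Event | Instruction | Worded as leaving the study? |
|---|---|---|
| Pneumonitis, any grade including 1 | 6.3.4 stops drug; 6.4.7 takes the patient off study | Yes |
| Intolerable grade 2 mucositis or other grade 3 toxicity, not recovered in 21 days | 6.3.2: withdrawn from the study | Yes |
| Need for a systemic antifungal | 6.4.4: off study | Yes |
| Grade 4 neutropenia, anemia or thrombocytopenia | 6.3.3: permanent stop of drug | No |
| AST or ALT grade 3 or higher | 6.3.2: permanent stop of drug | No |
| Grade 3 or higher skin toxicity or diarrhea | 6.3.2: permanent stop of drug | No |
| Any diagnosed infection | 6.4.2: permanent stop of drug | No |

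The split does not follow severity. Pneumonitis carries both wordings for one event, so the two terms are used interchangeably in places.

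**3. What under-counting does.** Assume a true adverse-event drug-stop rate of 20% and let only a share of those stops be counted. The effective rate is 20% × share.

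| Share counted (assumed) | Effective rate | Early | Early or final |
|---|---|---|---|
| 100% | 20% | 72.9% | 81.4% |
| 75% | 15% | 52.0% | 57.5% |
| 50% | 10% | 26.6% | 27.9% |
| 25% | 5% | 5.8% | 5.8% |

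**4. Infection, grade by grade.**
- Grade 3: 6.4.2 stops; 6.3.2 interrupts and restarts. This is a direct conflict.
- Grade 4: both stop, since 6.3.2 ends the drug for any other grade 4 event.
- Grades 1 and 2: 6.3.2 has no competing row, but the topical-antifungal allowance in 6.4.4 suggests that a local fungal infection need not end treatment, which is in tension with 6.4.2.
- Febrile neutropenia: 6.3.3 restarts the drug; if an infection is diagnosed, 6.4.2 forbids that.

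The documents give no infection rate, so the share of stops due to infection cannot be computed.

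**The case against.** The strongest reply on infection is that 6.4.2 is specific and unconditional while the 6.3.2 row is residual, so the specific instruction prevails. A grade 3 infection that needs hospitalization is also a serious adverse event, reviewed in real time under 13.1, which would limit unnoticed divergence. It may be added that the 6.3 tables cover only toxicity related to everolimus. The first two arguments have weight. But the protocol states no precedence, it does supply a pointer for pneumonitis, and 6.4.2 itself ties infection to the drug's immunosuppressive effect.

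On the toxicity rule, the reply is that the intent is clear enough and the vocabulary merely loose. Section 6.4.1 says of hepatitis B reactivation that "the trial will be immediately terminated and appropriate Hepatitis B therapy initiated", where the single patient's participation is probably meant; 1.5 likewise speaks of patients discontinuing the study. That supports counting every permanent stop. Yet 12.1 refers to events as defined in the protocol, and a narrower reading, confined to the events worded as leaving the study, is also open. A stopping rule should not rest on that choice.

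A reader might infer that the literal rule would count almost nobody. The text does not support this: three kinds of event are expressly worded as leaving the study. A reader might also infer that the infection conflict is confined to grade 3. Grade 3 is where it is clearest, but 6.4.4 and the febrile neutropenia row also sit badly with 6.4.2.

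Finally, the pause probabilities do not measure the infection conflict. That is correct. They show only how sensitive the boundary is to what is counted.

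**Conclusion.** Wrong as written, on both points; it should be amended. Following the 6.3.2 table to the letter can re-expose a patient to a drug that 6.4.2 says must be stopped for good. The event counted in 12.1 is undefined, and a literal count would be inconsistent and too low.

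The size of the infection effect is unknown. The effect of under-counting depends on an assumed share: at a 20% stop rate, the early pause probability falls from 73% with all stops counted to 27% with half counted. These figures assume independent patients with a common rate.

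Two stronger conclusions might be drawn and are not supported. The plan's probabilities are not in error; they are exact for whatever rate the counted event has. Nor does reaching the boundary end the trial. It triggers a pause and a review of all available data, with accrual halted until the DSMB accepts the outcome, so the consequence is limited.

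**What to change.** 1. In 6.3.2, add a row: *Infection, any grade: discontinue everolimus permanently (see 6.4.2)*. State that 6.4.2 takes precedence over the catch-all grade 3 row, and over the febrile neutropenia row in 6.3.3 when an infection is diagnosed. State that the antifungal bullet in 6.4.4 governs the choice of antifungal, not whether everolimus continues.
2. In 12.1, for both boundaries and in the probability statements, define the counted event as *permanent discontinuation of everolimus because of an adverse event, including adverse events for which this protocol says the patient is withdrawn from or taken off study*.
3. List infection stops by grade at the interim review.

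The cost is amendment wording. Sample size, boundaries and the stated 73%/6% and 81%/6% do not change, because they hold for the rate of the event so defined. The drawback is that mandated stops for mild infection then count towards the pause, so its actual probability may rise by an amount the documents do not allow one to estimate; item 3 lets the review weigh this. Whether to relax the any-grade stop is a clinical decision for the sponsor and is not part of this change.
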